14.2 Further Efficacy Endpoints

14.2.1 Confirmed objective response according to RECIST 1.1 as assessed by Investigator (Secondary endpoint)

Data collected in the eCRF for RECIST 1.1 response criteria as assessed by the Investigator (“Assessment of disease based on imaging (according to RECIST 1.1)” eCRF page) will be treated in the same way as data adjudicated by the IRC. Analyses described in section 14.1.1 will be repeated based on Investigator assessment, i.e.:

- Number and percentage of participants with Best Overall Response based on confirmed responses of CR, PR, SD, PD and NE and corresponding listing.
- The number and percentage of participants will be provided for Best Overall Response of CR or PR based on unconfirmed responses within 8 weeks before the cutoff. The participants will be taken into account only if their first CR or PR occurred within 8 weeks before the cutoff, they don't have confirmed response of CR or PR and they continue to have tumor assessments (they didn't discontinue the study for any reason and didn't discontinue treatment because of progressive disease). The denominator will be all participants in the analysis set.
- ORR and DCR will be provided with number and percentage of participants with their two-sided 95% CI using the Clopper-Pearson method (exact CI for a binomial proportion as computed by default by the FREQ procedure using the EXACT option). Analyses will be repeated for unconfirmed responses.
- Spider and Waterfall plots
- A summary table of the reasons for non-evaluable Best Overall Response based on confirmed responses and related listing, with the following reasons will be detailed:
 - No baseline assessment (if applicable)
 - No post-baseline assessments due to death within 8 weeks after the start of study treatment

- No post-baseline assessments due to other reasons
- All post-baseline assessments have overall response ‘Non-evaluable’
- New anticancer therapy started before first evaluable post-baseline assessment
- SD of insufficient duration (< 6 weeks after the start of study treatment)

Note: Special cases where Best Overall Response BOR is NE due to both early SD and late PD will be classified into this category

- No evaluable tumor assessment > 16 weeks followed by PD (i.e. tumor assessment of PD was > 16 weeks after start of study treatment and there was no evaluable tumor assessment in between)
- Not determined category may also be added if applicable
- Listing of reasons for non-evaluable Best Overall Response based on confirmed responses
- Listing of individual tumor assessments as well as listing of time point tumor response and overall response

In addition, a summary of the Best Overall Response based on confirmed responses and unconfirmed responses as adjudicated by IRC versus Investigator assessment will be provided including numbers of concordant and discordant assessments, and a listing of inconsistencies will be provided.

CCI

CCI

CCI

14.2.4 Progression-Free Survival (Secondary Endpoint)

Progression-Free Survival (PFS) time is defined as the time from first administration of study treatment until the first documentation of progression of disease (PD) or death due to any cause, whichever occur first.

$$\text{PFS} = (\text{date of PD or death or censoring} - \text{date of first administration of study treatment} + 1) / 30.4375 \text{ (months)}$$

The following censoring rules will also be applied for the PFS computation:

- Participants with no event (PD or death) will be censored on the date of the last adequate tumor assessment
- Participants who do not have a baseline tumor assessment or who do not have any evaluable post-baseline tumor assessments will be censored at the date of first administration of study treatment unless death occurred on or before the time of the second planned tumor assessment (i.e. 16 weeks) in which case the death will be considered an event.
- Participants who start new anticancer treatment prior to an event will be censored on the date of the last evaluable tumor assessment before anticancer therapy is given.

Note: any systemic anticancer therapy, any anticancer surgery and any anticancer radiotherapy will be considered as new/subsequent anticancer therapy and will lead to censoring.

- Participants with an event after two or more subsequent missing response assessments (i.e. no assessments in 112 days prior to the event during the first 12 months i.e. 365 days of follow-up or 168 days prior to the event after the first 12 months of follow-up) will be censored on the date of the last evaluable tumor assessment.

The last tumor assessment date is defined as the last available and evaluable tumor assessment performed prior to the cut-off date (or prior to end of study, i.e. participants lost to follow-up or who withdraw consent) or prior to subsequent anticancer therapy.

Censoring rules are also summarized in [Table 7](#).

Table 7 Censoring Rules for Analyses of PFS

Situation		Rule 1	Rule 2
No PD and no death	New anticancer therapy is not initiated	Censored at last tumor assessment*	Censored at last tumor assessment*
	New anticancer therapy is initiated	Censored at last tumor assessment* before new anticancer therapy	Censored at last tumor assessment*
No baseline assessment or no evaluable post-baseline assessment	No death or death > 16 weeks (112 days) after start of study treatment	Censored at date of first administration of study treatment	Censored at date of first administration of study treatment
	Death ≤ 16 weeks (112 days) after start of study treatment	Progressed at date of death	Progressed at date of death
PD or death	After ≤ 1 subsequent missing response assessment ^a	Progressed at date of documented PD or death, whichever came first	Progressed at date of documented PD or death, whichever came first
	After ≥ 2 subsequent missing response assessment ^a	Censored at last tumor assessment* before missing assessments.	Progressed at date of documented PD or death, whichever came first
	Before new anticancer therapy has started	Progressed at date of document PD or death, whichever came first	Progressed at date of documented PD or death, whichever came first
	After new anticancer therapy has started	Censored at last tumor assessment* before new anticancer therapy	Progressed at date of documented PD or death, whichever came first

Rule 1 used for PFS as assessed by the Investigator, by the IRC and for irPFS.

Rule 2 used for PFS counting all events (PD and death) regardless of the start of a new anticancer therapy and ignoring the number of missing evaluable tumor assessments before progression or death.

* with outcome CR, PR or SD. If no adequate tumor assessment, censored at date of first administration of study treatment.

^a No assessments in 112 days prior to the event during the first 12 months of follow-up or 168 days prior to the event after the first 12 months of follow-up.

The analysis of PFS as measured by the IRC (secondary endpoint) will be performed with a Kaplan-Meier method (product-limit estimates) and a summary of associated statistics will be

presented including corresponding two-sided 95% CIs. The CIs for the Med will be calculated according to Brookmeyer and Crowley (1982) and CIs for the survival function estimates will be derived using the log-log transformation according to Kalbfleisch and Prentice (1980) (CONFTYPE = loglog default option in SAS PROC LIFETEST). The estimate of standard error will be computed using Greenwood's formula.

Frequency (number and percentage) of participants with and without event and within each event type (PD or death) will be presented as well as the PFS Med, Min, and Max. Number of participants at risk, failed and PFS rates with their CI at 3, 6, 9, 12, 18 and 24 months will also be provided. Censoring reasons will also be described. Censoring reasons are as follows:

- Ongoing in the study without an event
- No baseline assessment
- No adequate post-baseline assessment
- Start of new anticancer therapy
- Event after 2 or more missing or non-evaluable post-baseline assessments
- Withdrawal of consent
- Lost to follow-up

Lost to follow-up will include the following participants:

- Lost to follow-up status is collected on the eCRF treatment termination page or eCRF study termination page prior to the analysis cut-off
- Participants with the last alive date > 14 weeks prior to the analysis cut-off date (duration of 14 weeks is based on the assessment schedule of every 3 months for survival follow-up interval + 2-weeks window)
- Participants who discontinued/completed the study without an event

PFS will also be presented graphically with Kaplan-Meier figures.

Listing will be provided with the following information: participant identifier, age, sex, race, date of first administration of study treatment, date of last tumor assessment, date of event/censoring, event/censoring reason, time to event.

CCI

CCI

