5.1 Inclusion Criteria

Participants are eligible to be included in the study only if all the following criteria apply:

Age

1. Are ≥ 18 years of age at the time of signing the informed consent. In Japan, if a participant is at least 18 but < 20 years of age, written informed consent from his/her parent or guardian will be required in addition to the participant's written consent.

Type of Participant and Disease Characteristics

2. Have a histologically documented advanced unresectable and/or metastatic cervical cancer (squamous cell carcinoma, adenocarcinoma, adenosquamous cell carcinoma) with disease progression during or after the prior platinum-containing chemotherapy:
 - a. The prior platinum-containing chemotherapy may be:
 - i. A systemic treatment for advanced unresectable, recurrent, persistent or metastatic disease or
 - ii. Treatment in the adjuvant or neo-adjuvant setting with disease progression or recurrence within 6 months of completion of platinum-containing chemotherapy.
 - b. Participants who previously only received platinum as a radiosensitizer are not eligible.
 - c. Participants must be naïve to checkpoint inhibitors (see Section 5.2).
3. Measurable disease outside the central nervous system (CNS) according to RECIST 1.1 at Screening. Evidence of measurable disease outside the CNS must be confirmed by IRC prior to start of treatment. Note: Lesions within the CNS are to be considered as non-target lesions only. Lesions may be considered measurable regardless of prior irradiation. Target lesions should preferably be selected from areas that have not been irradiated, or appear not to have been irradiated. If necessary, target lesion may be selected from areas that have been, or appear to have been irradiated in the opinion of the assessor.
4. Archival tumor tissue sample or newly obtained (preferred) core or excisional biopsy of a tumor lesion is mandatory and collected during the Screening period prior to enrollment. Fine needle aspirates are not acceptable. CCI
[REDACTED] If participant received local therapy (e.g., radiation therapy or chemoradiotherapy) after the archival tissue was taken, a new, acceptable biopsy will be required prior to study entry.
5. Have Eastern Cooperative Oncology Group (ECOG) PS of 0 to 1 at study entry and Day 1 of treatment with bintrafusp alfa.
6. Life expectancy ≥ 12 weeks as judged by the Investigator.
7. Have adequate organ function:

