PFS according to RECIST 1.1 assessed by an IRC	
PFS according to RECIST 1.1, is defined as the time from first administration of study intervention until date of the first documentation of PD or death due to any cause in the absence of documented PD, whichever occurs first.
 
PFS data will be censored on the date of the last adequate tumor assessment for participants who do not have an event (PD or death), for participants who start new anticancer treatment prior to an event, or for participants with an event after 2 or more missing tumor assessments. Participants who do not have a baseline tumor assessment or who do not have any post-baseline tumor assessments will be censored on the date of first administration of study intervention unless death occurred on or before the time of the second planned tumor assessment, in which case the death will be considered an event.
 
Kaplan-Meier estimates will be provided;
 
Median PFS and the 95% confidence interval for the median will be calculated according to Brookmeyer and Crowley (Brookmeyer 1982)

Overall survival	
Overall survival is defined as the time from first administration of study intervention to the date of death due to any cause. Participants last known to be alive will be censored at date of last contact.
 
Kaplan-Meier estimates will be provided;
 
Median OS and the 95% confidence interval for the median will be calculated according to Brookmeyer and Crowley (Brookmeyer 1982)

Confirmed Objective response, DOR, DRR, and PFS according to RECIST 1.1 assessed by Investigator	
Definition and analyses to be performed on the efficacy endpoints as assessed by Investigator will be similar to the endpoints as assessed by IRC, see above

Endpoint	Statistical Analysis Methods
CR= complete response, DOR= duration of response, DRR= durable response rate, IRC= Independent Review Committee, ORR= objective response rates, PFS= progression-free survival, PR= partial response, RECIST 1.1= Response Evaluation Criteria in Solid Tumors Version 1.1.	

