Further, split and coalesced lesions have to be taken into account appropriately to determine if a timepoint assessment is valid to derive the percent change from baseline in sum of diameters. All sum of diameters will be used, including the ones beyond first PD (for waterfall plot, the best post-baseline sum of diameters will be used even if occurring beyond PD). For waterfall plot, the percent change from baseline to 8-weeks assessment, as well as the percent change from baseline to the best post-baseline sum of diameters will be displayed for each participant.

The best percent change in sum of target lesion diameters will also be presented in a waterfall plot with confirmed Best Overall Response per IRC, histology, prior Bevacizumab use, prior anti-cancer radiotherapy, Moore criteria, number of prior treatment lines (0, 1 and ≥ 2) and PD-L1 expression at baseline measured by central lab (see section 8.2). A spider plot including all subjects with at least one target lesion previously irradiated will be provided. This plot will display the individual percentage of change in the sum of diameter since baseline for the target lesions previously irradiated and the curves will be color-coded to differentiate responder vs non-responder subjects.

Two listings of tumor assessment will be provided with the following information. First listing will display participant identifier, age, sex, race, first and last date of treatment, date of start of subsequent anticancer therapy, date of death when death occurs, visit, date(s) of imaging, description of target lesions (size, site, type, method), non-target lesions (status, site, type, method), and new lesions (site, type, method) and if the lesion split or merged. Second listing will present participant identifier, age, sex, race, first and last date of treatment, Best Overall Response based on confirmed responses, Best Overall Response based on unconfirmed responses, date of start of subsequent anticancer therapy, date of death when death occurs, target response, non-target response, new lesion, sum of diameters, % of change in sum of diameters since baseline and overall response.

In addition, a summary table of the reasons for non-evaluable Best Overall Response based on confirmed responses will be provided, the following reasons will be detailed:

- No baseline assessment (if applicable)
- No post-baseline assessments due to death within 8 weeks after the start of study treatment

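### SAP 14.2.4 and Table 7 define two missed assessments as a 112-day gap, but with 8-weekly scans that is the gap to a progression after one missed scan

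*SAP*

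**What the plan says.** Protocol 9.4.1, Table 12, censors PFS "for participants with an event after 2 or more missing tumor assessments" and gives no day count. SAP 14.2.4 keeps that rule and then translates it into days: "no assessments in 112 days prior to the event during the first 12 months", or 168 days for later events.

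Table 7 has two opposing rows. In the row "After ≤ 1 subsequent missing response assessment", Rule 1 counts the progression or death on its own date. In the row for two or more, Rule 1 censors at the last scan before the gap. Footnote a, attached to both rows, supplies the working definition: "No assessments in 112 days prior to the event during the first 12 months of follow-up or 168 days prior to the event" for later events.

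The imaging schedule is redacted, but the SAP shows it for the first year. Section 14.1.1 plots "the percent change from baseline to 8-weeks assessment", and 14.2.4 has a rule for the case that "death occurred on or before the time of the second planned tumor assessment (i.e. 16 weeks". Scans are therefore 56 days apart.

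On the baseline scan, protocol 5.1 (criterion 3) states: "Evidence of measurable disease outside the CNS must be confirmed by IRC prior to start of treatment". Appendix 9 allows that scan up to 4 weeks before treatment starts. Where there is no usable scan to censor at, Table 7 says: "If no adequate tumor assessment, censored at date of first administration of study treatment".

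Rule 1 governs PFS by IRC, PFS by Investigator and irPFS. SAP 14.2.8 applies the same censoring to DOR.

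**The concern.** A programmer will code the day count, not the verbal rule, and the two disagree for progressions. A progression is dated at a scan, so one missed scan already leaves a gap of two intervals. A cut-off of two intervals sits on the single-miss gap and leaves no room for scan windows.

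The result is that some IRC progressions that Table 7 calls events drop out of PFS and DOR. The table of censoring reasons would list them as events after two or more missed assessments, so it would not reveal the error. A participant who misses week 8 and progresses at week 16 could have a best overall response of PD (SAP 14.1.1 counts progression within 16 weeks) and yet be censored for PFS at first dose. A responder who progresses after 6 months could be censored back below 6 months and count as a DRR failure, so the bias is mostly but not always favourable.

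Rule 2 ignores missed assessments and would show the size of the effect. The visible list of analyses in SAP 6.1 names IRC PFS and DOR without it, although redacted text may include it.

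**Working it through.** **Inputs.** Interval of 56 days in year 1 (SAP 14.1.1 and 14.2.4). Baseline scan 1–28 days before first dose (protocol 5.1 and Appendix 9). The scan window is redacted, so 0, ±3 days (the visible visit window in protocol Table 1) and ±7 days are assumed. Timing deviations are taken as independent and uniform over whole days from −w to +w.

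**1. The plan's figures.** 2 × 56 = 112 days. 2 × 84 = 168 days, which suggests 12-weekly scans after the first year (inferred from this product only).

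**2. Gap to a progression after m missed scans.** Gap = (m + 1) × 56 + (j₂ − j₁), where j₁ and j₂ are the deviations of the last scan and the progression scan.

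| Missed scans | On schedule | ±3 days | ±7 days |
|---|---|---|---|
| 1 | 112 | 106–118 | 98–126 |
| 2 | 168 | 162–174 | 154–182 |

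**3. Share of single-miss progressions over 112 days, with an earlier post-baseline scan.** P(j₂ > j₁) = w / (2w + 1): 0 on schedule, 3/7 = 42.9% at ±3, 7/15 = 46.7% at ±7. The SAP does not say how a gap of exactly 112 days is treated. If it is censored, the share is (w + 1) / (2w + 1): 100%, 57.1% and 53.3%.

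**4. Week 8 missed, progression at week 16.** Run from a baseline scan k days before first dose, gap = 112 + k + j, with k = 1 to 28. On schedule that is 113–140 days, so 100% exceed 112 with no window assumed; with windows, 96.9% (±3) and 93.3% (±7). Run from first dose, the shares are 0%, 42.9% and 46.7%. The SAP does not state which start applies.

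**5. Deaths.** A death after one missed scan falls 56–112 days after the last scan, and after two missed scans at 112 days or more. For deaths, the day count fits the verbal rule.

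**6. Size, by simulation.** Assumptions: exponential PFS with the historical medians in protocol 2.2 (2.1 and 3.3 months), 20% of events deaths, 455 days of follow-up, scans missed at random, 40,000 simulated participants per cell scaled to 135. Single-miss progressions wrongly censored:

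| Gap run from | Timing | 5% missed | 15% missed |
|---|---|---|---|
| First dose | on schedule | 0 | 0 |
| First dose | ±3 or ±7 days | 3.0–3.6 | 7.7–8.9 |
| Baseline scan | on schedule | 2.7–3.7 | 7.5–9.4 |
| Baseline scan | ±3 or ±7 days | 4.7–5.2 | 12.0–13.5 |

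Six-month PFS rises by 0–1.0 point (first dose) or 0.3–2.0 points (baseline scan). For example, with a median of 3.3 months, 15% missed and ±7 days, 32.5% becomes 33.5% or 34.4%. The Kaplan-Meier median moves by −0.1 to +0.2 month, apart from one on-schedule case (3.7 to 4.2 months at 15% missed). Wherever any are wrongly censored, 64–92% of those labelled as two or more missed had missed one scan. A separate run with ±3 days, 5–10% missed and 15% deaths gave about 3–10 wrongly censored.

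**7. DOR.** Take 24% of 135, about 32 responders (the Phase I response rate), 50–80% with a progression, one scan missed and the next attended, and the shares from step 3 with windows. Low: 32 × 0.5 × 0.05 × 0.95 × 0.43 = 0.3. High: 32 × 0.8 × 0.15 × 0.85 × 0.47 = 1.5 responders.

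**The case against.** On a perfectly kept schedule, with exactly 112 days treated as acceptable, no single-miss progression between post-baseline scans is lost. Any error needs a timing deviation or the baseline-scan reading, and the scan window is redacted. That stands: the frequencies are illustrations, and only the day arithmetic is firm. Some slippage should still be expected, and the SAP itself adds a 2-week window when it sets its 14-week limit for loss to follow-up.

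The baseline-scan reading is arguably the weaker one. The neighbouring row of Table 7 counts 112 days from the start of treatment, and the censoring reason speaks of post-baseline assessments. That also stands, so the larger counts are an upper range. But the literal wording permits that reading. The row for participants with no evaluable post-baseline scan does not prevent it, because the progression scan is itself post-baseline.

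The protocol leaves further detail to the analysis plan, so the day count could be taken as the chosen definition of a missed assessment. It cannot be a faithful one for progressions, since it puts some single-miss cases into the row for two or more.

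Finally, PFS and DOR are descriptive estimates in a single arm, the tumour listing in the full SAP gives imaging dates from which gaps can be traced, and changing a censoring rule after cutoff can look data-driven. These points limit the consequence and shape the fix; they do not remove the contradiction.

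**Conclusion.** The concern holds. For progressions, the 112-day definition contradicts the two-or-more rule that it is meant to express, in both Table 7 and protocol Table 12, and should be corrected. The effect is small: 0 to about 9 of 135 participants wrongly censored if the gap runs from first dose, about 3 to 14 if it runs from the baseline scan, with 6-month PFS raised by at most about 2 points and 0.3–1.5 responders affected for DOR once windows are allowed. These counts depend on the assumed windows, miss rates, PFS distribution and response rate. The 8-weekly schedule is a firm inference from the SAP; the same flaw in the 168-day limit depends on later scans being 12-weekly. ORR does not use this rule and is unaffected.

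**What to change.** Preferably count missed scheduled assessments directly. Otherwise, for progressions only, set the limit at two scan intervals plus both scan windows: in year 1, more than 118 days for ±3 or more than 126 days for ±7. Either limit frees every single-miss progression (maximum 118 or 126 days) and still catches every two-miss progression (minimum 162 or 154). If later scans are 12-weekly, the ±3-day equivalent is more than 174 days (168 + 2 × 3). Keep 112 days for deaths.

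State that the gap runs from first dose when only the baseline scan precedes the progression. Widening the limit alone is not enough: measured from the baseline scan, 118 days would still censor about 79% of week-16 progressions after a single missed week-8 scan. Use one definition for PFS, irPFS and DOR, and add Rule 2 beside Rule 1 for PFS and DOR in the SAP 6.1 analysis if redacted text does not already do so.

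The cost is one clause in 14.2.4 and in footnote a, plus the Rule 2 rows. PFS and DOR may look slightly less favourable. SAP version 4.0 (21 February 2022) already postdates the 15 February 2022 cutoff, so record the change as made after cutoff and report results under both definitions.
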